### **8.12.2. Clinical Laboratory Evaluations**

Laboratory test results (hematology, serum chemistry, and urinalysis) at each scheduled visit and change from baseline will be summarized by treatment group.

Shift tables from baseline to each scheduled post-baseline visit will be provided for selected chemistry parameters (ALT, AST, total bilirubin, creatinine, creatine kinase, ALP, potassium) and hematology parameters (hematocrit, hemoglobin, platelets, white blood cell count and differential). For chemistry parameters, the following categories will be used: < the lower limit of normal (LLN), normal, > the upper limit of normal (ULN) to  $\leq 3 \times \text{ULN}$ ,  $> 3 \times \text{ULN}$  to  $\leq 5 \times \text{ULN}$ ,  $> 5 \times \text{ULN}$ , and missing. For hematology parameters, the following categories will be used: low, normal, high, and missing. Boxplots over time by treatment group of total white blood cell and absolute neutrophil counts will also be provided.

The number and percentage (based on the number of patients with a normal level at baseline) of patients in each treatment group with an ALT ( $> 3 \times \text{ULN}$ ,  $> 5 \times \text{ULN}$ , and  $> 10 \times \text{ULN}$ ), an AST ( $> 3 \times \text{ULN}$ ,  $> 5 \times \text{ULN}$ , and  $> 10 \times \text{ULN}$ ), an ALT or AST  $> 3 \times \text{ULN}$ , and a total bilirubin ( $> 1.5 \times \text{ULN}$  and  $> 2 \times \text{ULN}$ ) will be presented by study visit. A listing of patients who meet the laboratory criteria for Hy's law will also be provided. The laboratory criteria for Hy's law is defined as ALT or AST  $> 3 \times \text{ULN}$ , ALP  $\leq 2.0 \times \text{ULN}$ , and total bilirubin  $> 2 \times \text{ULN}$ . A listing will also be provided for the potentially clinically significant (PCS) values for the above parameters.

All clinical laboratory data will be listed. Values outside the normal ranges will be flagged.

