9.2.4 Analysis of Safety

All patients who receive any amount of study drug (Safety Population) will be included in the safety analyses. Patients who received the wrong study drug for their entire course of treatment will be analyzed in the group based on the drug received. Safety endpoints include the assessment of TEAEs and the evaluation of changes from baseline in safety laboratory test results, ECGs, vital signs, and physical examinations.

Adverse events will be coded using version 20.0 (or higher) of the Medical Dictionary for Regulatory Activities (MedDRA). The number and percentage of patients in each treatment group reporting at least 1 occurrence of a TEAE for each unique system organ class and preferred term will be tabulated. A TEAE is defined as an adverse event occurring on or after the administration of the first dose of study drug. Treatment-emergent adverse events will also be tabulated by treatment group, severity, and the relationship to study drug as assessed by the Investigator. The number and percentage of patients in each treatment group reporting at least 1 occurrence of a treatment-emergent SAE will be tabulated. The number and percentage of patients (in each treatment group) prematurely discontinuing study drug treatment due to a TEAE will be tabulated by system organ class and preferred term.

Safety laboratory data will be presented by descriptive statistics of the post-baseline value and the change from baseline, as well as the number and percentage of patients with potentially clinically significant laboratory values. Descriptive statistics of vital signs and ECG parameters and the change from baseline will also be presented. An outlier analysis of the ECG parameters will be conducted.

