# **8. STATISTICAL ANALYSIS**

## **8.1. General Statistical Considerations**

Summary statistics will be presented by treatment group. For continuous variables, the number of observations (n), mean, standard deviation, median, minimum, and maximum will be provided. For categorical variables, the frequency and percentage in each category will be displayed.

For summary statistics, the mean and median will be displayed to one decimal place greater than the original value and the measure of variability (e.g. standard deviation) will be displayed to two decimal places greater than the original value. All analyses will be performed using SAS® Version 9.3 or higher.

Descriptive statistics will be provided for each treatment group (ETX2514SUL and placebo [background imipenem/cilastatin therapy]). Statistical tests and/or confidence intervals (CIs) will be used to compare treatment groups.

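### The SAP does not carry through the protocol's count of patients with potentially clinically significant laboratory values: outside the liver tests there is no fixed-threshold incidence by arm, and no limits are stated

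*SAP*

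**What the plan says.** **Protocol.** Section 2.1 makes safety the primary objective. Section 9.2.4 says laboratory data will be shown as post-baseline values and changes, "as well as the number and percentage of patients with potentially clinically significant laboratory values". It names no analytes and gives no limits. Section 9.2 leaves the detail to the SAP.

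**SAP 8.12.2** plans the following:

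- For hematology, chemistry and urinalysis, results "at each scheduled visit and change from baseline will be summarized by treatment group".
- Shift tables from baseline to each scheduled visit for "selected chemistry parameters (ALT, AST, total bilirubin, creatinine, creatine kinase, ALP, potassium" and for hematocrit, hemoglobin, platelets, and white cells with differential.
- One set of bands for all the chemistry analytes: "For chemistry parameters, the following categories will be used: < the lower limit of normal (LLN), normal, > the upper limit of normal (ULN) to" 3xULN, then above 3 to 5xULN, then above 5xULN, and missing. For the blood counts: "For hematology parameters, the following categories will be used: low, normal, high, and missing".
- Threshold counts for liver tests only: "The number and percentage (based on the number of patients with a normal level at baseline) of patients in each treatment group" exceeding stated multiples of ULN for ALT, AST, ALT or AST, and total bilirubin, by study visit.
- A listing of patients who meet the laboratory criteria for Hy's law, followed by: "A listing will also be provided for the potentially clinically significant (PCS) values for the above parameters".

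SAP 8.1 sets the general rule: "Summary statistics will be presented by treatment group". No PCS limits appear in the visible SAP text. Its contents list ends at 8.14, with no PCS appendix and no section on changes from the protocol.

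**The concern.** The protocol promises a count of patients, and the SAP delivers a listing. A listing shows individual cases but gives no numerator, denominator or percentage by arm. Without stated limits it cannot be programmed unless someone chooses cut-offs later. It is also unclear which parameters the listing covers: the liver tests just named, the shift-table analytes, or every laboratory test.

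The shift tables might have filled the gap, but their chemistry bands are multiples of ULN. These suit enzymes and do not suit potassium, whose plausible range is narrow relative to its ULN. Creatinine is affected to a lesser degree, although Protocol 4.3 treats a post-baseline fall in creatinine clearance as needing confirmation and possible withdrawal.

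At stake is the most direct by-arm summary of individual laboratory outliers, in a trial of about 80 patients whose primary objective is safety.

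**Working it through.** The plan states no figure to reproduce here: Protocol 9.2.6 and SAP 4 say that no power calculation was done. The check compares the two documents and then tests the shift bands.

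**1. Coverage of the threshold counts (SAP 8.12.2).** There are 3 thresholds for ALT, 3 for AST, 1 for ALT or AST, and 2 for bilirubin: 3 + 3 + 1 + 2 = 9, on 3 analytes. The chemistry shift tables cover 7 analytes, so 7 − 3 = 4 have no threshold count: creatinine, creatine kinase, ALP and potassium. No hematology parameter has one. The liver counts are by visit and restricted to patients normal at baseline, so they too fall short of a count of patients with a PCS value at any time. Protocol exclusion 13 bars only AST or ALT above 3xULN, so a patient can enter above ULN and be outside that denominator.

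**2. Potassium bands.** The documents give no ULN, so I assume 4.8 to 5.5 mmol/L. Band start = multiple × ULN.

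| Assumed ULN (mmol/L) | 3xULN | 5xULN | 6.5 mmol/L as xULN | 7.0 mmol/L as xULN |
|---|---|---|---|---|
| 4.8 | 14.4 | 24.0 | 1.35 | 1.46 |
| 5.0 | 15.0 | 25.0 | 1.30 | 1.40 |
| 5.5 | 16.5 | 27.5 | 1.18 | 1.27 |

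The values 6.5 and 7.0 are illustrations, not proposed limits. Across the range the upper two bands will in practice be empty and every high value falls in one band. The table works as low/normal/high, with no grading in either direction.

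**3. Creatinine bands.** I assume a ULN of 1.0 to 1.4 mg/dL and a baseline of 0.7 to 1.1 mg/dL.

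- A doubling, as a multiple of ULN, is 2 × baseline / ULN. The lowest is 2 × 0.7 / 1.4 = 1.0 and the highest is 2 × 1.1 / 1.0 = 2.2. No doubling in this range passes 3xULN.
- The fold rise needed to pass 3xULN is 3 × ULN / baseline. The lowest is 3 × 1.0 / 1.1 = 2.7 and the highest is 3 × 1.4 / 0.7 = 6.0.

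**4. Number of patients involved.** With 80 patients at 2:1, the arms hold 80 × 2/3 ≈ 53 and 80 × 1/3 ≈ 27. The chance of at least one event is 1 − (1 − p)^n.

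| True rate p (illustrative) | n = 53 | n = 27 |
|---|---|---|
| 2% | 0.66 | 0.42 |
| 5% | 0.93 | 0.75 |

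At 5%, about 53.3 × 0.05 = 2.7 and 26.7 × 0.05 = 1.3 patients are expected. Events of this kind are likely to be seen, but so few patients may barely move an arm's mean.

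**The case against.** A reader might infer that the SAP removes by-arm counts of abnormal values altogether, or that laboratory shifts cannot be compared between arms. The documents support neither reading.

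- The liver counts are kept by treatment group at nine thresholds, and the PCS listing is an addition to them.
- Every hematology, chemistry and urinalysis result is summarized by arm and visit. SAP 8.1 includes the minimum and maximum for continuous variables, so each arm's extreme potassium and creatinine at each visit would be visible.
- Shift tables still separate low, normal and high for potassium, creatinine and hematology. The shift-table sentence does not itself mention treatment group, but the general rule in SAP 8.1 covers it. For creatine kinase and ALP, the 3x and 5xULN bands do grade severity by visit.
- Protocol 8.1 requires clinically significant laboratory abnormalities that arise or significantly worsen on study to be reported as adverse events, and SAP 8.12.1 tabulates treatment-emergent events by arm. By-arm counts of investigator-judged abnormalities are therefore planned.
- Protocol 9.2.4 names no analytes and Section 9.2 defers detail to the SAP. How many analytes to tabulate is partly a matter of choice.
- Re-banding potassium alone would only delete two empty columns.

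All of this stands, and it limits the point. None of it supplies the promised output. Adverse event reporting rests on investigator judgment, extremes do not say how many patients were affected, and by-visit shifts do not give the number of patients affected at any time. Leaving detail to the SAP permits it to choose analytes and limits, but the visible text sets no limits and offers no PCS count.

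**Conclusion.** The point holds as a minor gap between protocol and SAP. Protocol 9.2.4 commits to the number and percentage of patients with PCS laboratory values. SAP 8.12.2 gives fixed-threshold counts by arm for three liver analytes only, leaves PCS values to a listing of unclear scope, and states no limits. No such incidence is planned for creatinine, potassium, creatine kinase, ALP or hematology. The shift bands do not make up for this for potassium and do so poorly for creatinine.

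The loss goes no further than that. Laboratory data remain comparable by arm through summaries, shifts and adverse event tables. The potassium and creatinine figures rest on assumed reference limits, but the conclusion is the same across the ranges shown. The finding rests on the visible text: redacted passages are not counted as missing, and PCS limits held in another document would settle the question of definition though not the missing table.

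**What to change.** Before unblinding, amend SAP 8.12.2 to:

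1. State analyte-specific PCS limits, in both directions where relevant, for at least the chemistry and hematology parameters already in the shift tables.
2. Tabulate n (%) of patients meeting each limit at any post-baseline visit, by treatment group, in the Safety Population. SAP 8.12.4 already does this for maximum post-baseline QTcF.
3. State the denominator, for example patients with at least one post-baseline value, and say how patients already beyond the limit at baseline are handled.
4. Name the parameters that the PCS listing covers.

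The table should stay descriptive, since counts will be small. Collapsing potassium to low/normal/high is an optional tidy-up and does not replace items 1 and 2. If the sponsor prefers to keep only the listing, the SAP should record that as a change from Protocol 9.2.4 and give the reason.

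The cost is one paragraph of SAP text and a few table shells. The data are already collected, so no visit, sample or patient is added.

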9. Known seizure disorder requiring current treatment with anti-seizure medication which, in the opinion of the Investigator, would prohibit the patient from complying with the protocol. Patients with a history of epilepsy or who are on stable treatment (ie, no change in therapy within 30 days) with well controlled seizure disorder (ie, no recurrent episodes in the past 30 days) may be considered for enrollment in the study;
10. Treatment within 30 days prior to randomization with any cancer chemotherapy, immunosuppressive medications for transplantation, or medications for rejection of transplantation;
11. Patient requires continuing treatment with probenecid, methotrexate, ganciclovir, valproic acid, or divalproex sodium during the study;
12. Evidence of significant hepatic disease or dysfunction, including known acute viral hepatitis or hepatic encephalopathy;
13. Aspartate aminotransferase (AST) or alanine aminotransferase (ALT) $>3 \times$ ULN or total bilirubin $>2 \times$ ULN at Screening;
14. Receipt of a single dose of a long-acting, potentially-effective systemic antibiotic with activity against Gram-negative uropathogens for more than 24 hours within the 72-hour window prior to randomization. However, patients may enroll who:
 - Have received >48 hours of prior antimicrobial therapy, and (1) in the opinion of the Investigator, have failed that preceding antimicrobial therapy (ie, have worsening signs and symptoms), and (2) are documented to have a cUTI or AP that is caused by a pathogen resistant to the prior therapy, and (3) the causative pathogen is known not to be resistant (eg, the causative pathogen is either susceptible, intermediate, or unknown susceptibility) to imipenem;
 - Develop signs and symptoms of cUTI or AP while taking a systemic antibiotic for another indication (other than ETX2514SUL or imipenem/cilastatin), including antimicrobial prophylaxis for recurrent UTI; or
 - Received a single dose of a short-acting (ie, having a dosage frequency of more than once daily [eg, every 12 hours or more frequently]) systemic antibiotic up to 24 hours prior to randomization. No more than 25% of patients will be enrolled who meet this criterion;
15. Requirement at time of randomization for any reason for additional systemic antimicrobial therapy (including antibacterial, antimycobacterial, or antifungal therapy) other than study drug, with the exception of a single oral dose of any antifungal treatment for vaginal candidiasis;

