Clinically significant abnormal laboratory or other examination (eg, ECG) findings that are detected during the study or are present at Screening and significantly worsen during the study should be reported as adverse events. The Investigator will exercise his or her medical and scientific judgment in deciding whether an abnormal laboratory finding, or other abnormal assessment is clinically significant. Clinically significant abnormal laboratory values occurring during the clinical study will be followed until repeat tests return to normal, stabilize, or are no longer clinically significant. Any abnormal test that is determined to be an error does not require reporting as an adverse event.

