### **8.3. Baseline Definition**

For microbiological data, baseline pathogen(s) are determined from all specimens collected prior to the first dose of study drug.

For all efficacy and safety endpoints, baseline is defined as the last measurement or assessment prior to the first dose of study drug.

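### SAP 8.12.2 does not clearly deliver, for liver tests, the per-patient count of potentially clinically significant laboratory values that the protocol promises: its threshold table is by visit and uses a normal-baseline denominator

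*SAP*

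**What the plan says.** Protocol 9.2.4 commits the safety analysis to "the number and percentage of patients with potentially clinically significant laboratory values". It sets no limit by baseline level or by visit, but it also names no analytes or cut-offs.

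SAP 8.12.2 plans these liver outputs:

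- By-visit summaries of values and changes, by treatment group.
- Shift tables: "Shift tables from baseline to each scheduled post-baseline visit will be provided for selected chemistry parameters". These cover every baseline category. The top category is above 5 × ULN.
- A threshold table for ALT and AST (above 3, 5 and 10 × ULN), for ALT or AST (above 3 × ULN) and for total bilirubin (above 1.5 and 2 × ULN). Its base is given as "The number and percentage (based on the number of patients with a normal level at baseline", and the results "will be presented by study visit".
- Listings of patients meeting the Hy's law laboratory criteria, of all laboratory data, and of PCS values: "A listing will also be provided for the potentially clinically significant (PCS) values for the above parameters".

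For QTcF, SAP 8.12.4 takes each patient's maximum over all post-baseline evaluations and summarizes it by treatment group.

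**The concern.** Evaluating safety against placebo is the primary objective (Protocol 2.1), and Protocol 1.4 names hepatic dysfunction as a known sulbactam risk. The natural summary is the share of each arm that ever crossed a liver threshold. The protocol's PCS sentence points to a count of that kind, but in the SAP the term PCS is attached only to a listing. The one table of threshold counts is split by visit and rests on a narrower group than the protocol describes.

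If nothing is added, the report will not contain that share for either arm. It could be counted from the listings, but the denominator and the handling of unscheduled values would then be settled after unblinding.

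**Working it through.** The plan states no figure for this point, so there is none to reproduce. The check sets the planned outputs against the quantity wanted and then illustrates the gap.

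**Inputs.** About 80 patients at 2:1 (Protocol 9.2.6): 80 × 2/3 ≈ 53 on ETX2514SUL and 27 on placebo. Post-baseline chemistry is scheduled on Day 3, Day 5, Day 7, EOT, TOC and LFU (Protocol 8.6). That is six visits, or five where Day 7 is also the EOT Visit.

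**1. Does any planned output count each patient once, by arm, from measured values?**

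- Threshold table: by visit, with no any-visit or worst-value row.
- Shift tables: by scheduled visit. They have no 10 × ULN cut, no 1.5 or 2 × ULN cut for bilirubin, and no combined ALT-or-AST row.
- PCS and Hy's law: listings only.
- Adverse event tables (SAP 8.12.1): once per patient per preferred term, but an entry depends on the Investigator "deciding whether an abnormal laboratory finding, or other abnormal assessment is clinically significant".
- Serious adverse events: reporting is mandatory only when ALT or AST above 3 × ULN occurs with bilirubin above 2 × ULN (Protocol 8.10).

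None supplies the count.

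**2. Can the visit rows be combined?** No. One patient may cross at several visits, so the rows overlap by an unknown amount. Suppose 3 of 53 patients each cross a threshold once, and all have a normal baseline and are tested at every visit.

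- Per-patient incidence: 3/53 = 5.7%.
- Highest visit row if the crossings fall at three different visits: 1/53 = 1.9%.
- Highest visit row if they fall at the same visit: 3/53 = 5.7%.

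The same true incidence can therefore show as a peak row anywhere from 1.9% to 5.7%. With six such patients at different visits, it is 6/53 = 11.3% against 1.9%.

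**3. Who is outside the base?** Exclusion criterion 13 ("Aspartate aminotransferase (AST) or alanine aminotransferase (ALT" and so on) bars only ALT or AST above 3 × ULN or bilirubin above 2 × ULN at Screening. Lesser elevations are eligible. For the analysis, "baseline is defined as the last measurement or assessment prior to the first dose of study drug". The documents give no expected share with a raised baseline. Assumed shares of 10%, 20% and 30% would remove about 5, 11 and 16 ETX2514SUL patients and about 3, 5 and 8 placebo patients from the denominator.

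**4. Is the numerator restricted too?** The parenthesis fixes the base of the percentage and leaves the numerator open. Assume 10% raised baselines (53 − 5 = 48 remain), with one crossing in a normal-baseline patient and one in a raised-baseline patient at the same visit.

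- Matched numerator: 1/48 = 2.1%.
- Unrestricted numerator: 2/48 = 4.2%, which counts a patient who is not in the denominator.
- All patients: 2/53 = 3.8%.

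**The case against.** The strongest reply is that little is lost. The study is descriptive, has no power calculation and enrols about 80 patients. All laboratory values are listed, with separate PCS and Hy's law listings. Protocol 8.10 also requires a Liver Event Form whenever ALT or AST exceeds 3 × ULN or bilirubin exceeds 2 × ULN, so the main thresholds have a record triggered by the value itself and not by judgment. The cut-offs are already fixed in SAP 8.12.2, which leaves limited discretion in a later count. A normal-baseline table is a reasonable way to isolate new abnormalities. Elevations that persist across visits would also bring the visit rows close to the per-patient figure.

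Most of this stands, and it sets the priority. It does not supply the missing summary, because a listing or an event form is not a prespecified by-arm count.

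Three stronger readings are tempting, and the documents do not support them:

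- A reader might infer that no per-patient count was ever planned. Protocol 9.2.4 does plan one for PCS values and nothing withdraws it; the SAP does not clearly carry it out.
- A reader might infer that crossings are counted only in normal-baseline patients. SAP 8.12.2 says this of the denominator alone.
- A reader might infer that a difference of about 15 points between arms could go unseen. If each of five visits showed 2/53 against 1/27 (0.07 points apart), the per-patient difference could run from 2/53 − 5/27 = −14.7 to 10/53 − 1/27 = +15.2 points. That needs entirely different patients crossing at every visit in one arm and the same patients throughout in the other. It is an outer bound, not an expected size, and the listings would show every case.

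**Conclusion.** The point holds as a gap between protocol and SAP. The SAP does not clearly implement the promised by-arm PCS count for liver tests, and its threshold table cannot stand in for it, being by visit, on a normal-baseline denominator and with an unstated numerator rule. In the illustration, a true 5.7% could appear as no more than 1.9% at any visit. That rests on 53 patients, all with a normal baseline and tested throughout, and on crossings that do not overlap. The effect of raised baselines cannot be sized from the documents. Priority is modest: no case is concealed and no inferential result depends on it, but a simple summary serving the primary objective is missing.

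**What to change.** Add one table to SAP 8.12.2 for the Safety Population, by treatment group:

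- Each patient's worst post-baseline ALT, AST, ALT-or-AST and total bilirubin, at the thresholds already listed there.
- All scheduled and unscheduled values in the study database, as SAP 8.12.4 already does in principle for QTcF. State which local laboratory values count, because the documents do not say whether local repeats and standard-of-care results enter the database.
- Denominator: patients with at least one post-baseline value of that test, split by baseline category (normal; above ULN).
- A sentence identifying this as the liver part of the PCS count in Protocol 9.2.4.

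Keep the by-visit normal-baseline table as supportive, and state that its numerator is limited to the same patients as its denominator.

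The cost is one table shell and a few lines of text, with no new data collection. The drawback is that some crossings in raised-baseline patients will reflect small changes; the baseline split makes these visible.

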8.10 Safety Monitoring and Assessment of Abnormal Liver Function Tests

Management and discontinuation criteria for abnormal liver function tests (LFTs) have been designed to ensure patient safety and evaluate liver event etiology.¹⁰ Safety monitoring for LFTs will occur from randomization until 30 days following the last administration of study drug; however, any abnormal LFT will be monitored until the below criteria are met. Investigators should evaluate standard of care laboratory reports in addition to study laboratory reports when monitoring for LFTs.

Abnormal liver chemistry criteria:

The Investigator or sub-Investigator must review patient laboratory reports to identify if they meet the following criteria:

- Moderate abnormality:
 - AST or ALT $>3 \times$ ULN, or
 - Total bilirubin $>2 \times$ ULN.
- Severe abnormality:
 - AST or ALT $>3 \times$ ULN and total bilirubin $>2 \times$ ULN.

Action to be taken by Investigator:

If any 1 of the abnormal liver chemistry criteria is met, the Investigator or sub-Investigator must do the following:

- Obtain a detailed history of symptoms and prior or concurrent diseases. The Investigator should ensure that the medical history form captures any pre-existing illness that may be relevant in assessing hepatic function;
- Obtain a history of concomitant drug use (including over-the-counter/herbal/dietary supplements);
- Obtain a history of exposure to environmental chemical agents;
- Following the initial observed elevation, every effort should be made to have the patient reassessed within 48 hours to 72 hours. Repeat LFTs will be performed and sent to the central laboratory. Liver function tests may also be repeated via the local laboratory at the discretion of the Investigator;

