- Patients who have an Investigator-assessed, study drug-related elevation of their LFTs must be monitored 2 to 3 times per week until liver function chemistries (ALT, AST, alkaline phosphatase, and total bilirubin) completely return to normal range or return to the baseline level and associated clinical signs and symptoms return to baseline levels. If the elevation of LFTs is attributed to a non-study drug-related issue (eg, chronic hepatitis, chronic cholestasis, concomitant treatments, cardiovascular causes, etc.), the patient should be monitored until the LFTs stabilize or return to the patient's baseline level and associated clinical signs and symptoms return to baseline levels. The Investigator should contact the Medical Monitor to discuss additional management and follow-up of patients with elevation of LFTs;
- The event must be reported to [REDACTED] within 48 hours to 72 hours after its occurrence on a Liver Event Form;

- Consider a consultation with a specialist such as a hepatologist; and
- Consider performing liver imaging (ie, ultrasound, magnetic resonance imaging, computerized tomography).

Hy's Law definition:

The definition of Hy's Law is as follows:

1. Aspartate aminotransferase or ALT $>3 \times$ ULN,
2. Total bilirubin $>2 \times$ ULN, and
3. No evidence of intra- or extra-hepatic bilirubin obstruction (elevated alkaline phosphatase) or Gilbert's Syndrome.

If the first 2 criteria of Hy's Law are met, the case must be reported as an SAE.

Criteria for study drug discontinuation (severe hepatic abnormalities):

In the absence of an explanation for increased liver enzymes, the patient should be discontinued from the study drug. Discontinuation should be considered if:

- ALT or AST $>8 \times$ ULN;
- ALT or AST $>5 \times$ ULN for more than 2 weeks;
- AST or ALT $>3 \times$ ULN and total bilirubin $>2 \times$ ULN or international normalized ratio >1.5 ;
- AST or ALT $>3 \times$ ULN with signs or symptoms compatible with hepatitis or hypersensitivity (eg, fatigue, nausea, vomiting, right upper quadrant pain or tenderness, jaundice, fever, rash, or eosinophilia [$>5\%$]); or
- Close monitoring for a patient with moderate hepatic laboratory test abnormality is not possible.

Follow-up examination:

If any abnormal liver chemistry criteria are met, the following assessments should be obtained at the LFU Visit and documented in a Liver Event Form:

- Clinical symptoms course;

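### SAP 8.12.2 counts liver-threshold crossings visit by visit and only lists potentially clinically significant values, so no any-time (worst post-baseline) patient incidence by arm is planned

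*SAP*

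**What the plan says.** Protocol 9.2.4 says that laboratory data will be described by summary statistics, "as well as the number and percentage of patients with potentially clinically significant laboratory values".

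SAP 8.12.2 plans these by-arm outputs for the liver tests:

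- Patients with ALT or AST above 3, 5 and 10 x ULN, ALT-or-AST above 3 x ULN, and total bilirubin above 1.5 and 2 x ULN. Percentages are based on patients normal at baseline, and the counts "will be presented by study visit".
- "Shift tables from baseline to each scheduled post-baseline visit will be provided for selected chemistry parameters", including creatinine, and for hematology.
- A listing of patients meeting the laboratory criteria for Hy's law.
- "A listing will also be provided for the potentially clinically significant (PCS) values for the above parameters".

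SAP 8.12.4, by contrast, counts patients by their maximum QTcF over all post-baseline evaluations.

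Protocol 8.10 creates liver results outside the visit schedule. "Safety monitoring for LFTs will occur from randomization until 30 days following the last administration of study drug". After a qualifying elevation, "every effort should be made to have the patient reassessed within 48 hours to 72 hours", and "Repeat LFTs will be performed and sent to the central laboratory". Patients whose elevation the investigator attributes to study drug "must be monitored 2 to 3 times per week until liver function chemistries" are back to normal or baseline.

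**The concern.** Safety is the primary objective (Protocol 2.1), and Protocol 1.4 names hepatic dysfunction as a known risk of sulbactam. The first question a reader will ask is how many patients in each arm ever exceeded 3, 5 or 10 x ULN. A by-visit table does not answer it. The same cells can arise from one patient with a sustained elevation or from several patients with one elevation each, and these are different safety findings. If off-visit repeats are not assigned to a visit, a peak seen only on a repeat would also be missing from the table.

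**Working it through.** The documents give no figure to reproduce: there is no liver event rate, and the sample size rests on practical grounds. The check compares texts and shows what by-visit cells can and cannot determine.

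**Texts side by side**

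| Item | Planned presentation | Each patient counted once over all visits? |
|---|---|---|
| PCS laboratory values, Protocol 9.2.4 | Number and percentage of patients | Natural reading, not spelled out |
| Liver thresholds, SAP 8.12.2 | Number and percentage by arm at each visit | No |
| Shift tables, SAP 8.12.2 | Baseline to each scheduled visit | No |
| PCS values, SAP 8.12.2 | Listing | No count |
| QTcF, SAP 8.12.4 | Maximum over all post-baseline evaluations, by arm | Yes |

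Only one post-baseline ECG is scheduled (Protocol 8.8), whereas chemistry has 5 or 6 post-baseline draws. The worst-value summary is thus specified where it adds least. SAP 8.12.2 shows no redaction.

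**Inputs for the counting check**

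- About 80 patients randomized 2:1 (Protocol 9.2.6): 80 x 2/3 = 53 and 80 x 1/3 = 27, rounded.
- Post-baseline chemistry at Day 3, Day 5, Day 7, EOT, TOC and LFU (Protocol 8.6): 6 rows, or 5 if Day 7 is the EOT Visit.
- Assumption: all patients are dosed and normal at baseline, so the full arm is the denominator.

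**Bounds.** Let n_v be the number of patients above a threshold at visit v. For crossings seen at those visits:

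largest n_v ≤ patients who ever crossed ≤ sum of n_v (capped at the arm size).

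With one patient above 3 x ULN in each of 5 rows, the largest count is 1 and the sum is 5:

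- ETX2514SUL: 1/53 = 1.9% to 5/53 = 9.4%
- Placebo: 1/27 = 3.7% to 5/27 = 18.5%

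Conversely, suppose 5 of 53 patients truly crossed (9.4%). The largest by-visit cell could then be as low as 1/53 = 1.9%, if each crossed at a different visit, or as high as 9.4%, if all crossed at the same visit.

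**Off-visit repeats in a 7-day course.** If the recheck follows the draw by 2 to 3 days with no reporting delay:

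- A Day 3 draw is repeated on Days 5-6 and a Day 5 draw on Days 7-8. Either can coincide with a scheduled draw.
- A draw at EOT on Day 7 or 8 is repeated on Days 9-11. TOC, 6 to 8 days after EOT, falls on Days 13-16.
- A TOC draw is repeated at +2 to +3 days, and LFU falls at +5 to +9.
- An LFU draw has no later scheduled visit.

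The clock in Protocol 8.10 starts when the elevation is observed, and most draws go to a central laboratory. With an assumed 2 to 3 days of turnaround, the repeat of a TOC draw falls at +4 to +6 days and can meet LFU. How often a repeat falls off-visit therefore depends on a delay that the documents do not give. The repeat of an LFU draw is off-visit whatever the delay.

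**The case against.** **The SAP does count patients by arm.** A reader might infer that no by-arm patient count of liver crossings is planned. That is wrong: the count exists at each visit. Only the any-time count is absent.

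**The listing may be an extra.** The SAP says that a listing will also be provided, directly after the threshold table. On this reading the thresholds are the PCS criteria and the table already supplies the Protocol's count. Protocol 9.2.4 does not say any time or worst value. The reading is possible, so the documents do not support calling this an outright contradiction. However, the SAP never states its PCS criteria, and by-visit cells still do not give the number of patients with such a value.

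**Unscheduled results are not excluded.** A reader might infer that repeats are dropped from the threshold table. The SAP does not say so. It uses the word scheduled for the visit summaries and shift tables but not for the threshold counts. The point is silence, not exclusion.

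**What a repeat can add is limited.** A repeat follows a value already past 3 x ULN (2 x ULN for bilirubin). It can mainly add a higher category or a first crossing in another test.

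**Days 8 to 14 and the time after LFU.** A reader might infer that extended patients have only local chemistry between Day 7 and EOT, or that the weeks after LFU are a hole in this table. The first overlooks the central repeats that Protocol 8.10 requires after an elevation. The second is a matter of sampling, which a new table mostly does not change.

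**Other outputs carry the values.** Adverse event tables count each patient once. ALT or AST above 3 x ULN together with bilirubin above 2 x ULN must be reported as a serious event. Hy's law cases, PCS values and all laboratory data are listed, and with about 80 patients a hand recount is feasible. This stands and limits the harm. It is not a substitute, because adverse event reporting of laboratory values rests on investigator judgment, and an isolated ALT elevation does not meet the two-test rule.

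**Conclusion.** The concern holds in limited form. SAP 8.12.2 plans no any-time patient incidence by arm for the liver thresholds, which is the most direct delivery of the Protocol 9.2.4 commitment and the approach the SAP already takes for QTcF. It also leaves open whether repeat tests enter the table.

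The range of 1.9% to 9.4% (3.7% to 18.5% on placebo) illustrates what the cells leave undetermined under one assumed pattern. It does not predict event rates. If 1% to 10% of 80 patients crossed 3 x ULN (an assumption), between 0.8 and 8 patients would be concerned, and only some would peak between visits.

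Nothing here suggests that values are lost or that a safety signal would be hidden. The change is still worth making, because it serves the primary objective at little cost.

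**What to change.** Keep the by-visit tables and add to SAP 8.12.2:

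1. By arm, the number and percentage of patients whose worst post-baseline value exceeds each existing ALT, AST, ALT-or-AST and bilirubin threshold, with each patient counted once per threshold.
2. A rule that the worst value is taken over all scheduled and unscheduled results in the database, each expressed as a multiple of its own laboratory's ULN.
3. The denominator: all Safety Population patients with a post-baseline value, with the normal-at-baseline subset shown alongside. Exclusion criterion 13 admits ALT and AST up to 3 x ULN and bilirubin up to 2 x ULN, so the present denominator leaves out some patients with raised baseline values.
4. A worst post-baseline column in the shift tables, which also covers creatinine and the other selected parameters by category.
5. A sentence saying that the new table delivers the Protocol 9.2.4 count for the liver parameters.

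The cost is one paragraph, one table and one column, with no extra blood draws or data capture. There are two drawbacks. Local and central results are mixed, which the ULN scale only partly resolves. Patients tested more often also have more chances of a high worst value, so the by-visit tables should be read alongside.
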